**Possible:**

- Reasonable temporal relationship with investigational product use.
- Event could be explained by subject's clinical state or other factors.

**Probable:**

- Reasonable temporal relationship with investigational product use.

- Likely to be known reaction to agent or chemical group, or predicted by known pharmacology.
- Event cannot easily be explained by subject's clinical state or other factors.

**Definite:**

- Distinct temporal relationship with investigational product use.
- Known reaction to agent or chemical group, or predicted by known pharmacology.
- Event cannot be explained by subject's clinical state or other factors.

**8.3. PROCEDURES FOR AE REPORTING BY THE INVESTIGATOR**

AEs will be monitored throughout the study and will be recorded on the CRF with the date and time of onset, date and time of resolution, severity, seriousness, causality (relationship to use of investigational product), treatment required, and the outcome.

To elicit AEs, simple questions with minimal suggestions or implications should be used as the initial questions at all evaluation points during the trial. For example:

- How have you felt since your last assessment?
- Have you had any health problems since your last assessment?

The severity of each AE should be categorized as mild, moderate, or severe.

The causality of use of investigational product in relation to the AE will be assessed by the Principal Investigator after careful medical consideration and categorized as unrelated, unlikely, possible, probable, or definite.

If an AE occurs, the Investigator will institute support and/or treat as deemed appropriate. If a non-SAE is unresolved at the time of the last day of the study, an effort will be made to follow up until the AE is resolved or stabilized, the subject is lost to follow-up, or there is some other resolution of the event. The Investigator should make every attempt to follow SAEs to resolution.

**8.4. SERIOUS ADVERSE EVENT REPORTING BY THE INVESTIGATOR**

**Serious Adverse Event Reporting**

It is the responsibility of the Investigators or their designees to report any event of this nature to the sponsor or a designee within 24 hours of the event being brought to the Investigators' or their staffs' attention. It is also the responsibility of the Investigator to report all SAEs reported at their site to their Institutional Review Board (IRB), as required. The Investigator should make every attempt to follow all SAEs to resolution.

The following information should be provided when an SAE is reported to the sponsor or designee:

1. Protocol Number
1. Site Number
2. Subject Number
3. Subject Demographic information, including:
  - o Date of Birth
  - o Sex
  - o Race
4. Investigational product start date
5. Date of last dose of investigational product
6. Date investigational product reinitiated (if investigational product interrupted)
7. SAE information, including:
  - o SAE term (diagnosis only; if known or serious signs/symptoms)
  - o Description of SAE/narrative
  - o Date/time of onset
  - o Severity
  - o Outcome
  - o Date/time of resolution or death (if duration < 24 hours)
  - o Relationship to investigational product
  - o Action taken with investigational product
8. Criteria for classifying the event as serious, including whether the SAE:
  - o Resulted in death.
  - o Was life-threatening
  - o Required inpatient hospitalization.
  - o Prolonged inpatient hospitalization.
  - o Resulted in a persistent or significant incapacity or substantial disruption of the ability to conduct normal life functions.
  - o Was a congenital anomaly/birth defect
  - o Important medical events that may not result in death, were not life-threatening, or did not require hospitalization may be considered serious when, based upon appropriate medical judgment, they may jeopardize the patient or subject and may require medical or surgical intervention to prevent one of the outcomes listed in this definition. Examples of such medical events include allergic bronchospasm requiring intensive treatment in an emergency room or at home, blood dyscrasias or convulsions that do not result in inpatient hospitalization, or the development of drug dependency or drug abuse.
9. Concomitant medications
10. Relevant history

11. Possible causes of SAE other than investigational product
12. Copy of AE page from the CRF

**NOTE:** If an SAE occurs in any study involving KPI-121 0.25% ophthalmic suspension that is unexpected and is determined to be related or possibly related to investigational product, all sites will be notified by the sponsor and each site should report it to its IRB.

## 9. STATISTICS

### 9.1. STATISTICAL METHODS

Continuous measures (e.g., age) will be summarized descriptively by the mean, standard deviation, median, minimum and maximum values. Categorical measures will be summarized by the number and percent of subjects.

#### 9.1.1. Subject Disposition, Demographic and Background Characteristics

Subject disposition, demographic characteristics, and background variables will be summarized by study group.

#### 9.1.2. Analysis of Efficacy

The primary analysis population will be the Intent-to-Treat (ITT) population, defined as all subjects randomized. A subset of efficacy analyses will be examined for the Efficacy Evaluatable (EE) population, the definition of which will be outlined in the Statistical Analysis Plan and finalized prior to unmasking of study data pursuant to clinical data review.

The primary analysis of all ophthalmic efficacy measures will be based on the single study eye for each subject.

The co-primary endpoints are (1) the mean bulbar conjunctival hyperemia score at Visit 6; and (2) the mean [REDACTED] severity score averaged over the days from Visit 5 to the day before Visit 6.

Secondary and exploratory efficacy endpoints will be evaluated as elaborated in [Section 3](#).

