**Table 1: SUMMARY OF EFFICACY ENDPOINTS**  
**(All comparisons will be between the KPI-121 0.25% ophthalmic suspension and vehicle groups)**

Evaluation	Comparison	Visit	1°	2°	Exploratory
Conjunctival Hyperemia	Bulbar Mean values	6	X		
Conjunctival Hyperemia	Bulbar Mean values	4		X	
Conjunctival Hyperemia	Bulbar Mean change from baseline (BL)	4 vs. 2			X
Conjunctival Hyperemia	Bulbar Mean change from BL	6 vs. 2			X
		■			■
		■			■
		■			■
		■			■
		■			■
Severity	Mean values	5 through day before 6	X		
Severity	Mean values	3 through day before 4		X	
Severity	Mean change from BL	3 through day before 4 vs. Day -7 through Day -1			X
Severity	Mean change from BL	5 through day before 6 vs. Day -7 through Day -1			X
Frequency	Mean values	3 through day before 4			X

Evaluation	Comparison	Visit	1°	2°	Exploratory
	Frequency	Mean values	5 through day before 6		X
	Frequency	Mean change from BL	3 through day before 4 vs. Day -7 through Day -1		X
	Frequency	Mean change from BL	5 through day before 6 vs. Day -7 through Day -1		X
Corneal Fluorescein Staining	Mean values	4		X	
Corneal Fluorescein Staining	Mean values	6		X	
Corneal Fluorescein Staining	Mean change from BL	4 vs. 2			X
Corneal Fluorescein Staining	Mean change from BL	6 vs. 2			X
Lissamine Green Staining	Mean values	4			X
Lissamine Green Staining	Mean values	6			X
Lissamine Green Staining	Mean change from BL	4 vs. 2			X
Lissamine Green Staining	Mean change from BL	6 vs. 2			X
Subject-Rated Ocular Discomfort Severity Scores	Mean values	4			X
Subject-Rated Ocular Discomfort Severity Scores	Mean values	6			X
Subject-Rated Ocular Discomfort Severity Scores	Mean change from BL	4 vs. 2			X
Subject-Rated Ocular Discomfort Severity Scores	Mean change from BL	6 vs. 2			X

Evaluation	Comparison	Visit	1°	2°	Exploratory
Subject-Rated Ocular Discomfort Frequency Scores	Mean values	4			X
Subject-Rated Ocular Discomfort Frequency Scores	Mean values	6			X
Subject-Rated Ocular Discomfort Frequency Scores	Mean change from BL	4 vs. 2			X
Subject-Rated Ocular Discomfort Frequency Scores	Mean change from BL	6 vs. 2			X

CONFIDENTIAL

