### 3.5. DESCRIPTION OF TRIAL DESIGN

This is a Phase 2, multicenter, double-masked, randomized, vehicle-controlled, parallel-group study designed to evaluate the safety and efficacy of KPI-121 0.25% ophthalmic suspension in treating the signs and symptoms of dry eye disease.

This study will include up to 6 clinic visits, including 2 weeks of single-masked vehicle run-in followed by up to 28 days of investigational product dosing (KPI-121 0.25% ophthalmic suspension or vehicle).

Up to 400 subjects at up to 12 centers located in the United States (US) will be screened at Visit 1 (Screening). Subjects meeting eligibility criteria at this visit will enter a 14-day run-in period of QID dosing with single masked vehicle. At Visit 2 (Day 1/Randomization), approximately 150 subjects who continue to meet eligibility criteria will be randomized in an approximate 1:1 ratio to either KPI-121 0.25% ophthalmic suspension or vehicle dosed QID.

The study eye will be selected based on the study qualification criteria entered into the Interactive Web Response System (IWRS) for stratification at randomization. If both eyes qualify for the study with exactly the same values for ocular entry criteria, IWRS will choose the study eye as OD. Other randomization and stratification allocation criteria will be applied as elaborated in the data management plan. Randomization numbers will be automatically assigned to each subject as they are entered into the IWRS, based on the following 2 stratification criteria:

- Subject's day prior to Visit 2 (Day 1) [REDACTED] score [REDACTED]  
[REDACTED] AND
- Study eye baseline [REDACTED] bulbar conjunctival hyperemia score [REDACTED]

The IWRS will assign masked study kit numbers. Bottles of investigational product will be dispensed at designated visits based on the subject's randomization. The Sponsor,

Investigators, and study staff will be masked during the randomization process and through the remainder of the study.

Subjects will return to the clinic for complete study evaluation at Visits 4 and 6 (Day 15 ± 1 day and Day 29 ± 1 day, respectively). Subject will also return at Visits 3 and 5 (Days 8 ± 1 day and 22 ± 1 day, respectively) to [REDACTED]

[REDACTED] assess concomitant medication use and adverse events. Subjects will discontinue dosing and be released from the study at Visit 6 (Day 29 ± 1 day).

A summary of events is provided in [Appendix 1](#). Assessments in this study will include:

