## **9.2. SAMPLE SIZE ESTIMATION**

A sample size of 71 in each group will have 90% power to detect an effect size of █ using a 2-group t-test with a █ 2-sided significance level.

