## **9.3. LEVEL OF SIGNIFICANCE**

The primary assessment of the dose-response will be evaluated using a 5% level of significance. Since both co-primary endpoints will be required to be significant at the 0.05 level, there is no adjustment needed for multiple comparisons.

All other reported *p*-values will be considered descriptive and hypothesis generating.

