## **9.4. PROCEDURE FOR ACCOUNTING FOR MISSING, UNUSED, OR SPURIOUS DATA**

Any missing, unused, or spurious data will be noted in the final clinical study report. Multiple imputation will be employed to analyze incomplete data sets under the assumption that missing data are, at worst, characterized as missing at random (MAR). The reasons for missing data will be recorded and the impact of these reasons and any treatment group imbalance on the assumption of MAR will be evaluated. Imputation will be carried out only on the co-primary endpoints and time points.

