**APPENDIX 4: INVESTIGATOR-RATED ASSESSMENT OF BULBAR CONJUNCTIVAL HYPEREMIA**  
Investigators will rate bulbar conjunctival hyperemia at Visits 1, 2, 4, and 6 using the CCLRU Grading Scale.

- (0) None
- (1) Very Slight
- (2) Slight
- (3) Moderate
- (4) Severe

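### Section 9 names no model for the co-primary comparisons; the only test in the plan, an unadjusted t-test, would ignore baseline and both stratification factors and give up power

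*Combined protocol and SAP*

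**What the plan says.** Section 9.1.2 sets the ITT population and the single study eye as the basis for efficacy. It then states: "The co-primary endpoints are (1) the mean bulbar conjunctival hyperemia score at Visit 6". The second co-primary is a severity score averaged from Visit 5 until the day preceding Visit 6. No test, model, covariate or stratum follows.

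Other parts of the plan bear on this:

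- **9.2, sample size:** "A sample size of 71 in each group will have 90% power to detect an effect size of" a redacted value, "using a 2-group t-test with a" redacted two-sided level. This is the only test named in the plan.
- **9.3:** "Since both co-primary endpoints will be required to be significant at the 0.05 level", there is no multiplicity adjustment. Both endpoints must succeed.
- **9.4:** "Multiple imputation will be employed to analyze incomplete data sets", for the co-primaries only. The model fitted to each imputed data set is not named.
- **3.5:** "Randomization numbers will be automatically assigned to each subject as they are entered into the IWRS, based on the following 2 stratification criteria". These are a score from the day before Visit 2 (name partly redacted, probably severity) and study-eye baseline hyperemia.
- **Baselines exist for both outcomes.** Appendix 4: "Investigators will rate bulbar conjunctival hyperemia at Visits 1, 2, 4, and 6 using the CCLRU Grading Scale". Table 1 lists the severity change as "5 through day before 6 vs. Day -7 through Day -1", but change from baseline is exploratory only.

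**The concern.** Stratified randomization balances the arms on the stratification factors, so the difference in means varies less from trial to trial than under simple randomization. An unadjusted t-test does not see this. Its pooled standard deviation still contains the between-stratum variance, so its standard error is too large whenever the strata predict the outcome. It also leaves unused the further information in the baseline value itself.

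Because both endpoints must reach 0.05, a loss on each carries through to the probability that the trial succeeds. Leaving the model unstated also leaves open which analysis the multiple imputation in 9.4 feeds.

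**Working it through.** **Inputs.** From the documents: 71 per group and 90% power (9.2), 0.05 for each co-primary (9.3), 1:1 allocation and two stratification factors (3.5). Not available: the effect size and alpha in 9.2 and the stratum cut-points (redacted), and the baseline-outcome correlation r (not given). I take alpha as 0.05 two-sided and show r = 0.2, 0.3, 0.5 and 0.7.

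**1. The plan's own figure.** It cannot be reproduced exactly because inputs are redacted, so I solve for the implied standardized effect d. For a two-sample t-test the noncentrality is d√(n/2) = d√35.5 on 140 degrees of freedom. Setting power to 0.90 gives d = 0.548. A rounded d of 0.55 gives 71 per group and 90.2% power, so the statement is coherent for an unadjusted test. At alpha 0.025, d would be 0.597.

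**2. Conservatism of the t-test, analytically.** If the strata explain a share R² of outcome variance, the t-test's true type I error is about 2[1 − Φ(1.96/√(1 − R²))]. For a normal baseline split at its median, R² = 2r²/π.

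- r = 0.3: R² = 0.057; 1.96/0.971 = 2.02; type I error 4.4%
- r = 0.5: R² = 0.159; 1.96/0.917 = 2.14; type I error 3.3%
- r = 0.7: R² = 0.312; 1.96/0.829 = 2.36; type I error 1.8%

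**3. Power with baseline adjustment, analytically.** Residual variance is multiplied by 1 − r², so d becomes 0.548/√(1 − r²): 0.559, 0.574, 0.633 and 0.767 for the four values of r. Power at 71 per group is then 91.1%, 92.5%, 96.3% and 99.5%.

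**4. Simulation.** 10,000 trials per cell, n = 142, permuted blocks of 4 within four strata. The strata are median splits of the endpoint's own baseline and of a second factor correlated 0.3 with it. ANCOVA includes treatment, baseline and both strata.

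| r | Type I: t-test | Type I: ANCOVA | Power: t-test | Power: ANCOVA | Gain (points) | Extra width of t-test CI |
|---|---|---|---|---|---|---|
| 0.2 | 0.049 | 0.052 | 0.906 | 0.911 | 0.5 | 2% |
| 0.3 | 0.046 | 0.051 | 0.903 | 0.921 | 2 | 4% |
| 0.5 | 0.032 | 0.048 | 0.914 | 0.962 | 5 | 15% |
| 0.7 | 0.018 | 0.048 | 0.935 | 0.995 | 6 | 39% |

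The last column is the inverse of the ratio of reported standard errors, ANCOVA to t-test (0.983, 0.958, 0.869, 0.717). The t-test reports a mean standard error of 0.168 throughout, while its true value under the null is 0.165, 0.164, 0.153 and 0.138.

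**5. Both endpoints.** If they are independent and share the same r, power for both is the square of the per-endpoint power. From t-test to ANCOVA this is 82 to 83%, 82 to 85%, 84 to 93% (0.914² to 0.962²) and 87 to 99%.

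**6. Sensitivity.**

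- A second simulation gave t-test type I error of 4.2%, 3.3% and 1.9% at r = 0.3, 0.5 and 0.7. Power, t-test against ANCOVA, was 90.7 v 92.1%, 92.3 v 96.4% and 93.7 v 99.5%.
- At r = 0 the methods agree: type I error 5.3 v 5.2%, power 89.8 v 89.5%.
- With the own-baseline stratifier correlated only 0.8 with baseline and cut 70/30, the gains for the four values of r were 0.5, 2, 5.5 and 8 points.
- A three-grade discrete hyperemia baseline, entered with its own stratum, gave similar results.

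**The case against.** The strongest reply is that the t-test is named only to size the trial. Nothing says the co-primaries will be tested with it, and 9.1.2 and 9.5 refer to a separate Statistical Analysis Plan that may contain an adjusted model. This stands as a limit: the power loss is conditional on the t-test being used. What is certain is that Section 9 leaves the primary model open. Section 9.1.2 expressly sends only the efficacy-evaluable definition to that plan, and Section 3 and Table 1 describe the primary comparison as one of mean values.

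Second, the trial was sized on the unadjusted test, so its power stays at or above the stated 90% per endpoint in the table. That is correct. The loss is measured against the adjusted analysis, not against the design target.

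Third, r and the cut-points are unknown, and hyperemia is a 0 to 4 grade restricted by entry thresholds at Visits 1 and 2. A weak correlation is plausible there, and then the gain is only 0.5 to 2 points. The figures at r = 0.7 have no support in the documents beyond being possible.

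Fourth, hyperemia and a stratum cut from it may be nearly or wholly redundant. This does not harm the treatment estimate; a fully redundant term drops out.

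Finally, Table 1 does plan change-from-baseline comparisons for both co-primary variables. They are exploratory, and 9.3 makes their p-values descriptive, so they do not protect the primary test.

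**Conclusion.** The concern holds as a conditional one. Section 9 specifies no baseline or stratification adjustment for the co-primary comparisons, and the one test the plan names makes none. If that test is used and baseline is prognostic, it is conservative: type I error falls from 5% to about 3% at r = 0.5. It also gives up about 2 points of power per endpoint at r = 0.3 and 5 points at r = 0.5. There is no bias, no inflation of type I error and no shortfall against the stated 90%.

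The sizes rest on alpha 0.05, d = 0.548 solved from 9.2, an assumed r and assumed cut-points, so they are illustrative. The direction does not depend on these assumptions, provided baseline is prognostic. This should be changed because the improvement is nearly free, but it does not threaten the validity of the trial.

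**What to change.** In 9.1.2, and in the Statistical Analysis Plan it refers to, state the primary analysis before unmasking. Fit an ANCOVA for each co-primary endpoint with these terms:

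- treatment
- that endpoint's own baseline: study-eye hyperemia at Visit 2, or mean severity over Days -7 to -1
- the two stratification factors used in the IWRS

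Report the adjusted mean difference with a 95% confidence interval. Say that a stratification term wholly determined by the baseline covariate is dropped. In 9.4, name this as the model fitted within each imputed data set. Use the same structure for the secondary endpoints, each with its own baseline; those p-values remain descriptive.

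The cost is wording. No new data are needed. With two-level stratification factors the model uses three more degrees of freedom than the t-test: 142 − 5 = 137 instead of 142 − 2 = 140.

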#### 9.1.3. Analysis of Safety

Analysis of safety data will be presented for all subjects in the Safety population (i.e., all subjects receiving randomized investigational product). AEs will be coded using Medical Dictionary for Regulatory Activities (MedDRA, most current version) and categorized by system organ class using preferred terms. AEs will be tabulated by study group with respect to their Severity and relationship to the investigational product. Ophthalmoscopy findings will be summarized descriptively. IOP measurements, BCVA and Biomicroscopy will be summarized as safety outcomes.

## **9.2. SAMPLE SIZE ESTIMATION**

A sample size of 71 in each group will have 90% power to detect an effect size of █ using a 2-group t-test with a █ 2-sided significance level.

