**CONFIDENTIAL**

## SYNOPSIS

Study Title:	KPI-121-C-002: A Phase 2, Double-Masked, Randomized, Controlled Study of KPI-121 0.25% Ophthalmic Suspension Compared to Vehicle in Subjects with Dry Eye Disease
Objectives:	The primary objective of the study is to investigate the safety and efficacy of KPI-121 0.25% ophthalmic suspension compared to vehicle in subjects who have a documented clinical diagnosis of dry eye disease.
Study Population:	The study population will consist of subjects diagnosed with dry eye disease.
Number of Subjects	Up to 400 subjects who are diagnosed with dry eye disease will be screened. Among those screened, approximately 150 subjects will be randomized to KPI-121 0.25% ophthalmic suspension or vehicle.
Investigational Products:	KPI-121 0.25% ophthalmic suspension and vehicle will be supplied as investigational product.
Route and Duration of Administration:	1 to 2 drops of investigational product will be instilled in each eye four times per day (QID) for up to 28 days.
Study Design:	
This is a Phase 2, multi-center, double-masked, randomized, vehicle-controlled, parallel-group study designed to evaluate the safety and efficacy of KPI-121 0.25% ophthalmic suspension versus vehicle in subjects with dry eye disease.
 
Approximately 400 subjects will be screened and up to 150 subjects will be randomized at up to 12 centers located in the United States (US).
 
Subjects will be randomized to 1 of 2 study arms in an approximate 1:1 ratio. The study arms are: 1) KPI-121 0.25% ophthalmic suspension administered as 1-2 drops in each eye QID for up to 28 days or 2) vehicle administered as 1-2 drops in each eye QID for up to 28 days.
 
Furthermore, subjects will be assigned to a study arm based on the stratification of:
 

• Subject's day prior to Visit 2 (Day 1) [REDACTED] score

CONFIDENTIAL

- Study eye baseline investigator-rated bulbar conjunctival hyperemia score [REDACTED]

This study will include up to 6 clinic visits over 6 weeks. At Visit 1 Screening ( $14 \pm 1$  days prior to Day 1), subjects who meet screening inclusion/exclusion criteria will begin a 2-week run-in period during which they will be treated with 1-2 drops of single-masked vehicle in each eye QID for  $14 \pm 1$  days.

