## 5.3. SUBJECT WITHDRAWAL AND/OR DISCONTINUATION

Any subject who wishes to may withdraw from the investigational product use or from participation in the study of his or her own accord for any reason is entitled to do so without obligation. The Investigator may also withdraw any subject from the investigational product use or from study participation, if deemed necessary.

Investigational product use may be discontinued and any subject may be discontinued from study participation at any time during the study at the discretion of the Investigator or the sponsor for any reason including but not limited to:

1. Occurrence of any medical condition or circumstance that exposes the subject to substantial risk and/or does not allow the subject to adhere to the requirements of the protocol.
2. Any SAE, clinically significant AE, severe laboratory abnormality, intercurrent illness, or other medical condition that indicates to the Investigator that continued participation is not in the best interest of the subject.
3. Subject's decision to withdraw.
4. Any woman who becomes pregnant while participating in the study. Information on the pregnancy and outcome will be requested.
5. Subject's failure to comply with protocol requirements or study related procedures.
6. Termination of the study by the Sponsor, FDA, or other regulatory authorities.

In the event study discontinuation of a randomized subject is necessary, the Investigator should make every attempt to have subject complete Visit 6 assessments as possible. If a non-serious AE is unresolved at the time of the subject's final study visit, an effort will be made to follow up until the AE is resolved or stabilized, the subject is lost to follow-up, or there is some other resolution of the event. The Investigator should make every attempt to follow all serious adverse events (SAEs) to resolution. The reason for premature discontinuation should be entered onto the Case Report Form (CRF) and recorded in the subject chart.

Subjects who withdraw from the study will not be replaced.

Additionally, the trial or parts of the trial may be discontinued by the sponsor or at the recommendation of the Investigator after consultation with Kala Pharmaceuticals, Inc. This may be based on a significant number of AEs of a similar nature that warrant such action.

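### The 90% power in section 9.2 is for one t-test, but section 9.3 requires both co-primary endpoints to be significant, so 90% is not the power of the trial's own success rule

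*Combined protocol and SAP*

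**What the plan says.** Section 9.2 is one sentence: "A sample size of 71 in each group will have 90% power to detect an effect size of" a blacked-out value, for a two-group t-test at a blacked-out two-sided level. It does not say which endpoint the figure belongs to.

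Section 9.1.2 sets two co-primary endpoints. The first is hyperemia ("The co-primary endpoints are (1) the mean bulbar conjunctival hyperemia score at Visit 6"). The second is a subject-reported severity score averaged from Visit 5 to the day before Visit 6.

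Section 9.3 gives the success rule: "Since both co-primary endpoints will be required to be significant at the 0.05 level, there is no adjustment needed for multiple comparisons".

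Three other passages bear on the number that enters the calculation:
- **Number randomized.** Section 3.5 says "approximately 150 subjects who continue to meet eligibility criteria will be randomized in an approximate 1:1 ratio", which is about 75 per group. The Synopsis puts it as "up to 150 subjects will be randomized at up to 12 centers".
- **Analysis set.** Section 9.1.2 says "The primary analysis population will be the Intent-to-Treat (ITT) population, defined as all subjects randomized".
- **Missing data.** Section 9.4 plans multiple imputation: "Imputation will be carried out only on the co-primary endpoints and time points". Section 5.3 adds "Subjects who withdraw from the study will not be replaced".

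No legible passage gives the power to meet both endpoints, a correlation between them, or a separate effect size for each.

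**The concern.** Section 9.3 takes the both-must-win rule into account for type I error, where the rule costs nothing. Section 9.2 does not take it into account for power, where the rule has its cost. The probability that two tests both reject can never exceed the smaller of the two single-test powers, and it is lower than that unless the tests are almost perfectly correlated or one of them is almost certain to succeed.

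A reader who takes 90% as the trial's chance of success would expect a 10% chance of missing real effects on both endpoints. Under the most direct reading of the legible text the chance is larger. This affects how a split result, with one endpoint significant and the other not, would be interpreted at the end of the study.

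**Working it through.** **Inputs from the document**
- 71 per group, 90% power, one two-group t-test, two-sided (section 9.2).
- Both co-primary endpoints tested at 0.05 (section 9.3).
- About 150 randomized 1:1, so 150 / 2 = 75 per group (section 3.5).

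**Assumptions**
- Sizing level: blacked out in 9.2. Taken as 0.05, the level in 9.3, with 0.025 as the alternative.
- Effect size d (difference / SD): blacked out, so back-solved.
- Correlation rho between the two test statistics: not given. Shown at 0, 0.5 and 0.9.

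**Step 1. The plan's own figure.** Single-test power is P(T > t[1 - alpha/2; 2n - 2]), where T is noncentral t with 2n - 2 degrees of freedom and noncentrality d x sqrt(n/2). The other tail is negligible.

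At n = 71 and alpha = 0.05 the critical value is 1.977. Power of 90% requires d = 0.548, a noncentrality of 0.548 x sqrt(35.5) = 3.26. With d rounded to 0.55, power is 90.2% at 71 per group and 89.8% at 70, so 71 is exactly the number needed.

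At alpha = 0.025, 90% power requires d = 0.597. The rounded value 0.60 also needs exactly 71 per group. The stated figure therefore behaves as the power of a single test, and it is consistent with either sizing level.

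**Step 2. Power to meet both endpoints.** With single-test powers p1 and p2, and z(p) the standard normal quantile, joint power = Phi2(z(p1), z(p2); rho), the bivariate normal probability. Testing is at two-sided 0.05 throughout, whatever level was used for sizing.

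| Assumption | n per group | Single-test power at 0.05 | Joint, rho 0 | rho 0.5 | rho 0.9 |
|---|---|---|---|---|---|
| Sized at 0.05, d = 0.548 on both | 75 | 91.5% | 83.7% | 85.6% | 88.8% |
| Sized at 0.05, d = 0.548 on both | 71 | 90.0% | 81.0% | 83.2% | 86.9% |
| Sized at 0.025, d = 0.597 on both | 75 | 95.3% | 90.7% | 91.6% | 93.5% |
| Sized at 0.025, d = 0.597 on both | 71 | 94.2% | 88.7% | 89.9% | 92.1% |

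Hand check at rho = 0: 0.900 x 0.900 = 0.810, and 0.915 x 0.915 = 0.837.

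**Step 3. Unequal effects, sized at 0.05.** One endpoint keeps d = 0.548, and the other has the stated power at 71 per group.
- Other endpoint at 99% (d = 0.724): joint power 91-92% at 75 per group and 89-90% at 71.
- Other endpoint at 80% (d = 0.473): joint power 75-81% at 75 per group and 72-79% at 71.

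**Step 4. Which n applies.** The plan is for about 75 per group, with all randomized subjects analysed and the co-primary endpoints imputed. An effective 71 per group would mean a loss of information of (150 - 142) / 150 = 5.3%. The document states no dropout rate, so 75 is the planned case and 71 the case after that loss.

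**The case against.** The strongest reply is that nothing in 9.2 is false. The section states the power of one t-test and never calls it the power of the success rule, so sections 9.2 and 9.3 are compatible. That is correct. The point is an incomplete statement of power, not an arithmetic error.

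The second reply is that the shortfall may not exist, and this also stands. The sponsor may have sized at a stricter level, or chosen an effect size with the joint rule in mind. An effect of about 0.607 on each endpoint, tested at 0.05, gives 90% joint power at 71 per group even with independent endpoints. The extra subjects above 142 also help. In the equal-effects case sized at 0.05, though, the full 75 per group still leaves joint power below 90% up to a correlation of 0.9.

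A reader might infer that the trial is underpowered or should enrol more subjects. The documents do not support that. The sizing level and effect size are blacked out, the correlation is not given, and plausible values put joint power on either side of 90%. Nor can the blacked-out values be held against the plan, since the sponsor has them.

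A reader might also infer that requiring both endpoints at 0.05 without adjustment inflates type I error. It does not: because both tests must succeed, each can be run at the full level.

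Finally, this is a Phase 2 study, and the correction would not alter its conduct or analysis. That bears on severity, and is why the point is rated minor.

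**Conclusion.** The point holds as a mismatch between the stated power and the success rule. The 90% in section 9.2 is the power of one test, while section 9.3 requires two, and no legible passage gives the power of that joint rule.

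Its size is conditional. If sizing used two-sided 0.05 and both endpoints have the planning effect, joint power is about 84-89% at the planned 75 per group and 81-87% at 71. The chance of missing the success rule despite real effects on both is then 11-16% or 13-19%, rather than 10%. With sizing at 0.025, joint power is 91-94% at 75 per group and 89-92% at 71. That, or an endpoint with power near 99%, leaves little or no shortfall. A weaker second endpoint would make the gap larger.

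Severity is minor. Confidence is high in the mismatch, and does not extend to the size of any shortfall.

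**What to change.** In section 9.2:
1. Label the 90% as the power of a single co-primary test and name the endpoint it refers to.
2. Restate the trial's power as the power to meet both co-primary endpoints at two-sided 0.05. The sponsor should compute this from its own effect size for each endpoint, over a stated range of correlations, and say which number per group it uses.

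The cost is a change of wording and one calculated range. No extra subjects are requested, and the design, alpha and decision rule stay as they are. The only downside is that the stated power may look less favourable.
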